## **13. Ethics/Protection of Human Subjects**

This study is to be conducted according to applicable US federal regulations and institutional policies (which are based in federal regulations, guidance, and ICH Good Clinical Practice guidelines).

*Consent Process*

If agreeable, families of children who are identified with a behavioral health concerns during a primary care visit - either through a positive behavioral screen or parental concern - will be referred to the study. Referral and consent can occur through two different pathways:

**Pathway 1 Warm handoff:** This pathway will be utilized when the FP is available to meet with the family in a private space at the time that the concern is identified. The FP will meet with the family, explain the study, and obtain written consent, child assent (with explanation of the study offered to children ages 2 and older in an age appropriate manner) and obtain HIPAA authorization.

**Pathway 2 Telephone outreach:** If the FP is not available to meet with the family, she will reach out to the family within 24 hours of receiving an internal referral. For these families, we are requesting approval for verbal consent for study participation and a waiver of child assent. We will obtain written HIPAA authorization when families are seen later in person and prior to obtaining additional PHI.

In both cases The PCP (or integrated behavioral health clinician) will complete an internal referral form using the health center's internal referral mechanism in EPIC (electronic medical record). This mechanism, which is accessed through EPIC's orders module is already utilized to refer families to health center-based ancillary services, including behavioral health and case management. We will work with DotHouse Health IT to develop a new referral form, similar to one that we have used in our autism study, Project Early. [SEE SAMPLE TEXT] for the current study. The completed form will be routed to the FP, as a record of permission to contact.

**SAMPLE INTERNAL TEXT**

This is an internal referral that will enable your patient to be referred to the Navigation research study and connected one of the Navigation Project's Family Partners.

**Eligibility:** Children ages 3-12 years who have a positive behavioral health screen or parental concern about their child's behavior or mental health

**Purpose:** To test different ways to support engagement in behavioral health services

**Benefits:** Family will be provided assistance to connect with behavioral health services

**Compensation:** None

**Child's Name:**

**Child DOB**

**Parent/Guardian Name:**

**Phone Number:**

**Best time to call:**

**Language Preference:**

Reason for referral:

As a pragmatic trial, the overall goal is to align referral and consent as closely as possible with existing workflows to reduce staff burden and support sustainability. Therefore, PCP will complete the internal referral form in EPIC for any patient who 1) the PCP thinks would be eligible for the study based on inclusion criteria, and 2) family agrees to have their information shared with the FP (research staff). To ensure that the rights of families are honored, we will educate pediatric clinician about referral procedures, emphasizing the need for families to give permission for the FP to contact them.

We are requesting a HIPAA waiver for the use of the internal referral form for contacting potentially eligible families. It would be impractical to obtain a signed HIPAA consent from all eligible families given the busy CHC clinical work flow and the pragmatic nature of this trial. However, research staff will need to access a limited number of identifiers in order to later contact the referred families. Specifically, the following identifiers are needed: MRN (to access chart), name, DOB (to confirm age eligibility) and phone number. All identifiable information associated with the internal referral form will be transmitted, stored, analyzed, or otherwise exist only in EPIC, a HIPAA-compliant electronic system that meet the standards for protection of PHI at DotHouse. The referral form and the associated PHI will remain in EPIC and in the child's medical record. If identifiers are in any case taken from the referral form, printed or recorded on paper, it will be destroyed as soon as eligibility has been determined for potential subjects.

If during the discussion with the FP, the parent states that s/he is not interested in seeking behavioral services at this time, the FP will ask the parent if she can reach out to them in ~ 3 months to see if services for the child are desired at a later date. If upon recontacting the family, they would like services and would like to work with the FP, the family will have the opportunity to enroll in the study and be randomized to a study condition. This group of parents will be called the "watchful waiting" group. We have included this group based on our clinical experience. We find that many families wish to delay services for a number of reasons including life events (family moving, expecting a new baby) and timing (child going away for the summer, want services through school and school ending or not in session). We would like to make study participation available for such families.

Only after the consent process is complete will the child and family be randomized. For parents who have more than one eligible child that participants, all children will be assigned to the same random condition.

We will use the parent consent form version which includes both parent and child as subjects of the study. We will conduct verbal consent if patient is contacted by phone (See Consent Form--Verbal) or written consent and assent if the initial visit with the parent is in person. For parents who have more than one eligible child they would like to participate, we will obtain a consent form for each unique child.

The study will recruit children between 3 and 12 years of age and a designated parent/ guardian for each child. One parent may consent more than one child into the study. It will not involve prisoners or institutionalized individuals. The study could involve two populations considered to be vulnerable: pregnant women and children.

Pregnant women. Although the study will not specifically target pregnant women, given that the study enrolls young children and their families, it is possible that a mother could be pregnant. Such women will not be excluded. Women of childbearing potential will be entitled the same protections as listed above. We foresee no extra risk of the study for a woman of child bearing potential than it is to anyone else.

Children. This research targets children, and their caregiver/legal guardian, who are being offered FN supports for accessing behavioral health services. Parents between the ages of 16-21, who are the legal guardians of the child referred for assessment, will not be excluded based on age; thus, it is possible that we will enroll parents who are under 21. Young parents often face additional barriers accessing health services for their children. For this reason and according to state law in the jurisdictions where the study will be implemented, we plan to enroll parents in this age group in the study. We have enrolled such parents in previous studies, which were reviewed and approved by the Boston University Medical Center IRB, without any adverse events. Therefore, we are confident that protocols for the proposed research will be ethical and lawful, and will be approved by the participating institutions' IRB.

For children who are enrolled in the study as participants, we will assure that the investigative team has the appropriate expertise to conduct research with children. All of the investigators are licensed clinicians and are mandated reporters of child abuse and neglect. Family Partners will be parents themselves; thus, they will have extensive experience working with children. As part of family partner training, [name] and [name] will provide training on working with the families of children with behavioral healthcare needs, as well as mandated reporting procedures and management of emergency situation. All facilities used in the study will be appropriate for children, as these facilities will be either families' homes or pediatric healthcare sites.

In addition, we will obtain formal assent from children for whom the study consenting process is done in-person during a clinic visit based on their cognitive ability to understand that their parent is seeking assistance to find services to help address their behavioral or emotional concerns.

For the children for whom assent is appropriate, we will explain the study in simple terms appropriate for child's developmental level. We expect that the detail of this explanation will vary given the age range of eligible children. The primary points that we will make sure all children understand are:

1. this research study involves helping their parent(s) find behavioral or mental health services that they believe will be helpful for their child;
2. families will get different combinations of assistance; the exact combination will be decided randomly - like flipping a coin;
3. the FP will assist their parent connect to services but will not be providing any direct services to the child;
4. participation is voluntary and their parent can decide to stop at any time without any negative consequence.

We will not obtain assent from children for whom the study consenting process is done via telephone. As a pragmatic trial, we believe that it is not practical to do obtain child assent when the consenting process is done via phone. It is very likely that the child will not be present at the time of parental consent - e.g. child is at school; child is playing elsewhere; parent and child are not in same location. In addition, parents routinely make final decisions about what is in the best interest of their child's health, thus the rights and welfare of the child are sufficiently protected by only having the parent consent.

Optimizing a Paraprofessional, Family Partner Navigation Model for Children  
Version 1.2, September 20, 2023

This protocol and any amendments will be submitted to the Boston Medical Center and Boston University Medical Campus IRB, for formal approval of the study conduct. The decision of the IRB concerning the conduct of the study will be made in writing to the investigator. A copy of the initial IRB approval letter will be provided to the sponsor before commencement of this study.

*Protecting right of withdrawal*

The study team will stress that participation in the study is entirely voluntary, that participants will be permitted to withdraw consent and leave the study at any time without incurring any negative effect on their care. Potential participants will be also told that they are free to take breaks and/or terminate the consent process. If at any time the potential participant is not interested in the study, the team will thank them for taking the time to hear about the study and then record information about why they were not interested in participating.

## Appendices

### Appendix A. Schedule of Events/Timeline for Child and Patient during Intervention

Months	Baseline	1	2	3	4	5	6	7	8	9	10	11	12
Behavioral Health Screening	x	x											
Index Visit with FP	x	x											
Randomization	x	x											
Referral to behavioral health	x												
First appointment with behavioral health (target within 90 days)													
Retention in Services measured ≥4 visits or resolution					x								
Intervention delivery including coordination and meeting with FP based on needs/ plan and by randomized strategies													
Family Resources Tracking	x							x					x
Child Symptoms Tracking TAU	x						x						x
Child Symptom Tracking Enhanced	x			x			x			x			x
Parent Capacity (PHQ2)	x			x			x			x			x
Tracking Resources Use and Care coordination Activities (EHR FP Template)		x	x	x	x	x	x	x	x	x	x	x	x
Client Satisfaction Questionnaire						x							x
Satisfaction with Navigator						x							

### Appendix B. Schedule of Events/Timeline.

Table 4. Timeline	YEAR 1				YEAR 2				YEAR 3			
	1	2	3	4	1	2	3	4	1	2	3	4
QUARTER												
Hire and train FPs and research staff	x	x										
Work with clinic EHR to create reports, templates, integrate surveys	x	x										
Finalize procedures, manuals, and protocols	x	x										
Participant enrollment			N= 50		N= 152			N= 202				
Intervention delivery			x	x	x	x	x	x	x	x	x	x
Follow-up assessments					x	x	x	x	x	x	x	x
Outcomes analysis												
Implementation analysis					x	x	x	x	x	x	x	x

The first 6 months will include start-up activities—setting up workflow for baseline screening and data collection protocol; hiring/training FPs and study staff; and protocols for mitigating contamination between conditions. We will also work with IT staff at DotHouse, with input from our consultant ([name]), to modify the EHR as needed. We will begin participant enrollment at 6-months, continue with 12 months of follow-up for all study participants, and end with the last 6 months dedicated to data analysis and manuscript preparation.

#### 1. Introduction

---

This Charter is for the Data and Safety Monitoring Board (DSMB) for the study titled: **Optimizing a Paraprofessional, Family Partner Navigation Model for Children**

The National Institute of Mental Health (NIMH) requires that all clinical trials include a DSMB Charter. Furthermore. Because this project includes a clinical intervention, a vulnerable population, and a verbal consent, the inclusion of a Data and Safety Monitoring Plan and Board is appropriate. The DSMB will include an independent group of experts on child and family behavioral health, clinical trials, and biostatistics, who will advise and monitor the project with the study principal investigator ([name]). None of the members will directly supervise, report to, or directly collaborate with the PIs. The DSMB will meet every six months. Its primary responsibilities will be to: 1) review and evaluate the accumulated study data for participant safety, study conduct and progress, and efficacy; and 2) make recommendations concerning the continuation, modification, or termination of the trial. In this proposed project the DSMB will consider: study-specific data and any concerns for poor clinical outcomes among patients in a particular randomization condition.

The Charter is intended to be a living document. The DSMB may wish to review it at regular intervals to determine whether any changes in procedure are needed.

#### 2. Responsibilities of the DSMB

---

The DSMB is responsible for safeguarding the interests of study participants, assessing the safety and efficacy of study procedures, and for monitoring the overall conduct of the study. The DSMB is an independent group advisory to the investigators of the study, and is required to provide recommendations about starting, continuing, and stopping the study. In addition, the DSMB is asked to make recommendations, as appropriate, to the NIEHS about:

- Efficacy of the study intervention
- Benefit/risk ratio of procedures and participant burden
- Selection, recruitment, and retention of participants
- Adherence to protocol requirements
- Completeness, quality, and analysis of measurements
- Amendments to the study protocol and consent forms
- Participant safety, and
- Notification of and referral for abnormal findings

### 3. Organization and Interactions

---

The following illustrates the relationship between the DSMB and the study investigators.

Communication with DSMB members will be primarily through the principal investigator (PI), [name]. It is expected that other study investigators will not communicate with DSMB members about the study directly, except when making presentations or responding to questions at DSMB meetings or during conference calls.

### 4. DSMB Members

---

DSMB members and their expertise are listed in Appendix A. Program Staff involved in the study, and their responsibilities are listed in Appendix B. The Project Manager (PM) will provide an unbiased staff interface for the DSMB, especially during executive sessions. The PM is responsible for assuring the accuracy and timely transmission of the final recommendations and DSMB minutes.

### 5. Scheduling, Timing, and Organization of Meetings

---

DSMB meetings are usually held by remote connections. The purpose of the first meeting is to review and discuss this Charter, to provide an overview of study activities, to review and make recommendations about the protocol(s), and to determine the frequency of interim analyses and whether data will or will not be masked to identity of randomized groups. Enrollment in a study cannot begin until the DSMB's Charter has been accepted, and IRB approval has been obtained.

Meetings will be approximately twice a year, with additional meetings or conference calls scheduled as needed.

- For this DSMB, meetings and calls will be held: every 6 months, with the first at the beginning of the study and prior to the first randomization of study participants.
- Review of interim data analyses will occur: every 6 months

The agenda for DSMB meetings and calls may be drafted by the study Project Manager (PM). The PM will finalize the agenda after consultation with the DSMB Chair. The agenda and meeting materials should be distributed by the PM 2 week[s] before each meeting or call.

Before each meeting, when the agenda is sent out, the PM will ask all DSMB members to state whether they have developed any new conflicts of interest since the last formal annual report. If a new conflict is reported, the Chair and other members will determine if the conflict limits the ability of the DSMB member to participate in the discussion, and whether further evaluation of the BMC ethics officer for intramural studies, is warranted. The DSMB also will review adverse event data, other safety data, enrollment data, and quality and completeness of study data at each meeting to ensure proper trial

conduct. At intervals, as noted above, the DSMB will also review formal interim analyses of the primary end point.

It is expected that all DSMB members will attend every meeting and call. However, it is recognized that this may not always be possible. Quorum for voting is considered to be half the number of standing members plus one. The Board may wish to decide if particular expertise is needed within the quorum for the meeting to be valid. All standing Monitoring Board members are voting members. The Board may also wish to decide in advance whether *ad hoc* members can vote.

## 6. Discussion of Confidential Material

---

DSMB meetings and calls will be organized into open, closed, and executive sessions.

- During the **open sessions**, information will be presented to the DSMB by the PIs and PM as appropriate, with time for discussion.
- During the **closed sessions**, the DSMB, PIs, PMs, if appropriate and approved by the Chair, will discuss confidential data from the study, including information on efficacy and safety. The DSMB will decide whether to remain masked to the treatment assignments at each meeting.
- The DSMB may elect to hold an **executive session** in which generally only the DSMB members are present in order to discuss study issues independently.

If the **closed or executive session** occurs on a conference call or video connection, steps will be taken to ensure that only the appropriate participants are on the call, and to invite others to re-join the call only at the conclusion of the executive session.

At the conclusion of the **closed or executive** sessions, the participants will be re-convened so that the DSMB Chair can provide a summary of the DSMB's recommendations. This provides an opportunity for study investigators to ask questions to clarify the recommendations. The meeting is then adjourned.

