## 4.2 Study Outcome Measures (See Table 1)

### 4.2.1 Primary Outcome Measures

#### Objective 1: To identify the most effective strategy to deliver FN

**Our primary outcome measure is receipt of behavioral health services within 90 days (yes/no)** will be defined as first encounter with behavioral health services within 90 days of randomization obtained from the electronic health record including Family Partner's template documentation.

Related to this primary objective, we will evaluate *time-to-receipt of behavioral health services* defined as time from randomization to first behavioral health service encounter obtained from the electronic health record, including family partner's template documentation. Dates will be obtained from administrative and billing data (electronic health records) for services within DotHouse, and FP documentation for services outside the health center.

A second primary outcome includes change in child symptoms over time.

- Pediatric Symptom Checklist-17 (PSC-17). A 17-item psychosocial screen designed to recognize cognitive, emotional, and behavioral problems. Three subscale Internalizing, Attention, and Externalizing have specific cutoffs and provide additional guidance regarding need for further follow-up. PSC-17 is embedded in the Epic (electronic health record) as a self-scoring form. It is widely used and has been validated in diverse populations.
- The Survey of Wellbeing of Young Children (SWYC). The SWYC screens for cognitive, motor, language, and social-emotional development among children up to 5½ years of age. We will track behavioral symptoms using the SWYC's Preschool Pediatric Symptom Checklist (PPSC), an 18-item questionnaire that has demonstrated strong concurrent validity with the Child Behavior Checklist (CBCL) and parents' reports of socio-emotional diagnoses as well as acceptability in diverse populations. Translations are available in a range of languages and the SWYC is currently being incorporated into the Epic system used at DotHouse.

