### DATA AND SAFETY MONITORING PLAN

Because this project is a clinical trial, includes a clinical intervention, Family Navigation, and aims to enroll a vulnerable population, the inclusion of a Data and Safety Monitoring Plan and Board is appropriate and required by the funder, NIMH. The Data and Safety Monitoring Board (DSMB) will include an independent group of experts on child behavioral health, clinical trials, and biostatistics, who will advise and monitor the project with the study principal investigator ([name]). None of the members will directly supervise, report to, or directly collaborate with the PIs. The DSMB will meet every six months. Its primary responsibilities will be to: 1) review and evaluate the accumulated study data for participant safety, study conduct and progress, and efficacy; and 2) make recommendations concerning the continuation, modification, or termination of the trial. In this proposed project the DSMB will consider: study-specific data and any concerns for poor clinical outcomes among patients in a particular randomization condition.

As part of their responsibility, DSMB members will ensure the timeliness, completeness, and accuracy of the data submitted to them for review. Members will ensure submitted data are sufficient for evaluation of the safety and welfare of study participants. The DSMB will also assess the performance of overall study operations and any other relevant issues, as necessary.

Specific items to be reviewed by the DSMB will include:

- Interim/cumulative data for evidence of study-related adverse events;
- Interim/cumulative data for evidence of efficacy according to pre-established statistical guidelines;
- Data quality, completeness, and timeliness;
- Adequacy of compliance with goals for recruitment and retention, including those related to the participation of women and minorities;

- Adherence to the protocol;
- Factors that might affect the study outcome or compromise the confidentiality of the trial data; and
- Factors external to the study such as scientific or therapeutic developments that may impact participant safety or the ethics of the study.

After each meeting of the DSMB, members will meet without the study PIs and provide them with a written letter of recommendations. (See Appendix C for DSMB charter)

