## 8. Reports to the DSMB

---

For each meeting, the PM will prepare summary reports and tables to facilitate the oversight role of the DSMB. The DSMB should discuss at the first or subsequent meetings what data they wish to review and how it should be presented.

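### The DSMB charter leaves a route by which comparative interim results can reach the PIs and the project manager of an unblinded trial

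*Combined protocol and SAP*

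**What the plan says.** The rules are in the DSMB charter (Appendix C) and in protocol section 10.2.

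- **Closed sessions (charter section 6):** "the DSMB, PIs, PMs, if appropriate and approved by the Chair, will discuss confidential data from the study, including information on efficacy and safety". On masking, the section adds: "The DSMB will decide whether to remain masked to the treatment assignments at each meeting". A members' executive session is optional.
- **Interim data (charter section 5):** "Review of interim data analyses will occur: every 6 months". At those intervals "the DSMB will also review formal interim analyses of the primary end point".
- **Remit (protocol section 10.2):** the board considers "any concerns for poor clinical outcomes among patients in a particular randomization condition".
- **Project manager:** charter section 8 says that for each meeting "the PM will prepare summary reports and tables to facilitate the oversight role of the DSMB". Section 5 has the project manager send out the meeting materials. Section 4 makes this person the board's staff contact, executive sessions included. Section 7 adds responsibility for minutes that summarise the discussion and are sent to the PI.
- **Meeting without the PIs (protocol section 10.2):** "After each meeting of the DSMB, members will meet without the study PIs". They then send the PIs a letter of recommendations.

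Outside the board, protocol section 5 has the project manager review Family Partner contact logs and health-record reports each month for contamination between conditions. Section 6.1 has the PIs and the navigation supervisor train the Family Partners. Section 4.2.1 takes service dates outside DotHouse from "FP documentation for services outside the health center".

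**The concern.** A closed session exists so that comparative results stay with people who cannot influence the trial. This charter allows people with operational roles into that session, and it gives one of them the tables and the minutes. No independent statistician or other firewall is named.

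The trial has few barriers further down. Two Family Partners deliver the intervention (section 3.1). They obtain consent (section 9), run the assignment program (section 5), know the condition and record part of the primary outcome. If it became known that one level of a factor looked better, effort, supervision or record-keeping could shift by condition while families were still being enrolled and followed. All four factor contrasts rest on the same staff and the same outcome, so each would be exposed.

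**Working it through.** The plan gives no figure on this point, so the check sets the provisions side by side.

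**Step 1. Channels out of the board.**

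| Channel | Who has access | Content | Safeguard stated | Charter section |
|---|---|---|---|---|
| Closed session | PIs, project manager | Confidential efficacy and safety data | Must be appropriate and approved by the Chair; no criterion given | 6 |
| Tables and meeting materials | Project manager | Whatever the board asks to see | None | 5, 8 |
| Executive session | Project manager, as staff contact | The board's independent discussion | Members only as a general rule; session optional | 4, 6 |
| Minutes | Project manager, then PI | Key points of the debate, and recommendations | Chair signs or approves; closed content is not separated from open | 7 |

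The sentence in section 6 can be read with the Chair's approval attached to the PIs and the project manager, or to the project manager alone. I take the first reading, which is kinder to the plan. Even so, approval governs only the first row. Under section 7 the minutes reach the PI within 7 days, or within 2 days if concerns are raised.

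**Step 2. Whether the content can be comparative.** Pooled figures would reveal nothing about the factors. But an interim efficacy analysis of the primary end point compares factor levels, and the remit to look for poor outcomes in one condition needs data split by condition, at least under codes. Masking is raised at the first meeting (section 5) and left to the board at each meeting (section 6). Unmasked review by condition is therefore permitted but not required. If the board stays masked, nothing says that whoever builds the tables is masked too.

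**Step 3. Frequency.** One review every 6 months is 12 / 6 = 2 a year. The first meeting precedes the first randomization (section 5), so it carries no outcome data.

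**Step 4. From the recipients to the outcome.** The project manager sees the Family Partners' logs monthly, and the PIs train them. The Family Partners attend no board session. For results to affect the outcome they must travel one step further, through those working contacts. The documents neither describe nor bar that step.

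**Step 5. What might close the route.**

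- The members' meeting in protocol section 10.2 comes after each meeting. It does not keep the PIs out of the closed session before it, and it does not mention the project manager.
- Section 11.2 cross-checks the health record against accountable-care billing data, which cover services outside DotHouse. Section 4.2.1 takes DotHouse dates from administrative and billing data. Both limit biased recording. Neither touches a real difference in effort, because a service obtained through extra effort is a true event.
- Section 10.4 says there are no stopping rules. Interim efficacy review is still scheduled, so the information still exists.

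**The case against.** The best defence is that the charter only permits these things. Attendance needs the Chair's approval, the board may stay masked, it decides which data it sees and how (section 8), and it meets without the PIs after each meeting. Charter section 3 expects investigators other than the PI to have no direct contact with members about the study except to present or answer questions. Most Family Partner training falls in the start-up period (Appendix B), before interim data exist. The two Family Partners already see which families reach services and can form their own impressions by condition.

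Much of this stands, and it rules out three stronger readings.

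- A reader might infer that the PIs and project manager will routinely see results by condition. The text makes both attendance and unmasking discretionary.
- A reader might infer that those admitted are the people who enrol families and supervise the Family Partners. Family Partners obtain consent and run assignment, and they are not admitted. Their named supervision is by a supervisor and a co-investigator (section 5), neither of whom is shown to be admitted. The supportable links are training by the PIs and log review by the project manager.
- A reader might infer that only the executive session excludes the PIs. Protocol section 10.2 provides a further meeting without them.

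The defence does not reach the tables, the executive-session role or the minutes, none of which depends on the Chair's approval of attendance. Nor are a Family Partner's impressions from their own cases equivalent to a formal analysis across all families.

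**Conclusion.** The charter leaves an unguarded route for interim comparative results to reach the PIs and the project manager. It should be closed. The project manager's part is the firmer half, since it rests on assigned tasks; the PIs' attendance rests on a conditional permission, although their receipt of the minutes does not.

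The size of any bias cannot be calculated from the documents. The opportunity recurs twice a year once outcome data exist. Harm requires that reports be split by condition, that labels be disclosed or worked out, and that the knowledge then alter conduct. The plan allows the first two and does not guard against the third. Nothing shows that any disclosure has occurred. Biased recording could be partly checked against billing data; differential effort could not be corrected afterwards.

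**What to change.** Amend the charter, which section 1 says may be revised.

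- **Section 6:** limit closed sessions to board members and the reporting statistician. PIs and the project manager attend open sessions on pooled data, where the board can put questions to them.
- **Section 8:** any table by condition goes directly from the statistician to the board. The project manager keeps the pooled reports.
- **Section 4:** remove the project manager from executive sessions.
- **Section 7:** separate open from closed minutes. Withhold the closed minutes from the PI and project manager until the trial ends and send them only the recommendations, which matches the letter in protocol section 10.2. Section 7 now has the PI forward the minutes to the IRB, so it should say that the open minutes and recommendations take that route.

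The cost is charter wording and a reassigned task. Protocol section 9 mentions a study statistician, but only as holding the randomization generator; independence from the final analysis is not shown. That person would become unblinded to interim results, so the final analysis plan should be fixed before the first unmasked report. A separate statistician would be a stronger safeguard at greater cost.
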